6.3. Considerations during the COVID-19 pandemic

During the COVID-19 pandemic, patients will be enrolled at the Investigator's discretion considering patient's benefit and risk and the availability of staff at the study sites. The Sponsor will perform a risk assessment of the study on an ongoing basis and prioritize patient safety to ensure:

- The protection of patient safety, particularly if scheduled visits to the site are postponed
- The uninterrupted supply of drug to patients who continue to benefit from it, while assuring safety, even if they are encouraged to remain at home (guidance will be provided to the site)
- The collection of safety and efficacy data, even if patients cannot keep their scheduled visits to the study site.

The following considerations may be applied in accordance with individual site policies and guidelines from regulatory authorities ([FDA 2021](#), [EMA 2021](#)). The Sponsor will continue to follow regulatory guidelines for any updates related to the COVID-19 pandemic. If planned on-site monitoring visits are no longer possible, the Sponsor will consider optimizing the use of central and/or remote monitoring programs to maintain oversight of study sites. Alternative approaches will be implemented to maintain patient safety and study data quality and integrity, such as enhanced central monitoring, telephone contact with the sites to review study procedures, patient status and study progress, or remote monitoring of individual enrolled patients, where appropriate and feasible.

- If a patient is unable to sign the informed consent in person, their consent may be obtained electronically or remotely via phone call or video call.
- If a patient is unable to attend a scheduled on-site study visit and/or complete any protocol-required study assessments, the Sponsor should be contacted for further review.
- To ensure compliance with the protocol-required laboratory tests and assessments, the possibility for these tests to be performed at a local qualified laboratory or facility will be evaluated. The results of any tests or assessments performed by a local laboratory or facility must be communicated to the Investigator and documented in the patient's source files and the eCRF.
- If it is not possible to have assessments performed at a local facility, the patient may be evaluated for safety via a phone call or video call, assuring the collection and follow-up of adverse events is documented in the patient's source file. All C1 assessments need to be performed. For C2 and beyond, a patient will not receive additional treatment without having laboratory and ECG assessments performed at least once during each cycle (eg, on C1D1).
- Response assessments will need to be performed, as often as the circumstances allow, according to the protocol. If the patient is not able to visit the study site, alternatively, a local qualified imaging facility can be used.

- The results, including the images obtained from all radiographic procedures, should be sent to the Investigator. The imaging facility used, the timepoints, and the Investigator's review of the images should be documented in the patient's source files and the eCRF.
- If a patient is diagnosed with COVID-19 or develops symptoms suggesting COVID-19, patients will be managed according to local guidelines. Symptomatic COVID-19 cases will be reported as AEs or SAEs; it is at the Investigator's discretion to report asymptomatic COVID-19 cases. In the case of patients diagnosed with COVID-19 (symptomatic or asymptomatic), patients can only continue treatment with futibatinib if the Investigator considers that there is an individual positive risk/benefit balance, and once the patient has fully recovered from the COVID-19 infection. The Sponsor should be made aware of the Investigator's decision.

7. PHARMACOKINETICS

The PK population will consist of all patients who received at least one dose of futibatinib and have evaluable PK data for analysis. Blood samples will be obtained from all patients at the timepoints listed in [Table 10](#) and used to determine plasma futibatinib concentrations.

In the event that a patient interrupts treatment after the pre-dose sample is collected and restarts the treatment at a later date, a pre-dose sample should be collected.

Table 10: Pharmacokinetic Blood Sample Collection

Day of Study (Time Window)	Collection Time Point (hours) in Relation to Futibatinib Administration (Time Window)
Day 15 of Cycle 1 (\pm 3 days)	Pre-dose (from -30 min to just before dose)
	1 hour \pm 30 min post-dose
	3 hours \pm 30 min post-dose

8. EFFICACY EVALUATIONS

8.1. Cohorts A and B

8.1.1. Efficacy Criteria

For patients in Cohorts A and B, response assessments (including CT/MRI) will be performed by the Investigator/local radiologist according to RECIST 1.1 guidelines ([Eisenhauer et al. 2009](#)). Planned time points for all efficacy assessments are provided in the [Schedule of Events](#).

Results of the local assessments, including response for target and non-target lesions and appearance of new lesions, will be the basis for the continuation or discontinuation of study drug decisions.

If the Investigator determines that a patient has developed clinical disease progression manifested by symptomatic deterioration but not supported by radiologic evidence of progression, the patient may stop treatment. Symptoms of clinical disease progression must be documented in the patient's source documents and must be reported as AEs. Every effort should be made to document objective disease progression even after discontinuation of treatment.

Note that patients who discontinue without documented disease progression should continue to undergo response assessments/scans according to the Schedule of Events until PD is documented, new anticancer therapy is initiated, the study is terminated, or consent is withdrawn.

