Prior & concomitant medications, AE assessments		→													
Physical examination	X	X				X		X	X		Within 24 hours prior to dosing.				
Vital signs	X	X				X		X	X		Heart rate, blood pressure, body temperature, and respiration rate.				
Height and weight	X	X				X		X	X		Height at screening only.				
ECOG performance status	X	X				X		X	X		Within 24 hours prior to dosing.				
12-Lead electrocardiogram	X	X				X		X	X						
Hematology	X	X	X	X	X	X		X	X		Within 24 hours prior to dosing. More frequent assessments may be performed if clinically indicated				
Coagulation	X	X				X		X	X		Within 24 hours prior to dosing.				
Chemistry (serum or plasma)	X	X	X	X	X	X		X	X		Within 24 hours prior to dosing.				

Evaluation	Screening (Within 28 days of 1 st dose)	Treatment Period (1 cycle =28 days)						Notes	
		Cycle 1			Cycle ≥2				
		D1 (±3 days)	D8 (±3 days)	D15 (±3 days)	D22 (±3 days)	D1 (±3 days)	End of Cycle (±7 days)		
Pregnancy test	X Within 7 days						X		Serum pregnancy test required for WOCBP. Additional testing may be required by local regulations.
Ophthalmological examination	X			See Note					Examination to be performed by an ophthalmologist or qualified delegate at screening, 4-6 weeks after first dose, and as indicated if symptoms or signs of mineral deposits.
PK blood sampling				See Note					Pre-dose (from -30 min to just before dose), 1 h±30 min post-dose, and 3 h±30 min post-dose
ctDNA blood samples	X						X		
Tumor tissue sample	X								Archival or fresh tumor biopsy
Response assessments (CT/MRI)	X						X	X	At baseline and the end of every 2 cycles ±7 days), or as clinically indicated, until radiologic PD or initiation of new anticancer therapy (whichever comes first). For patients who discontinue treatment for reasons other than radiographic disease progression, imaging will be performed at EOT, (if the prior scan was performed ≥9 weeks) and during Survival Follow-up until radiologic disease progression or initiation of new anticancer therapy (whichever occurs first) unless patient withdraws consent.
Survival status								X	For all patients, unless patient withdraws consent or the study is terminated early by the Sponsor.

Table 2: Schedule of Events (Cohort C)

Evaluation	Screening (Within 28 days of 1 st dose)	Treatment Period (1 cycle =28 days)						End of Treatment (+7 days)	Safety Follow-up 30 days after last dose (+7 days)	Survival Follow-up Period (every 12±2 weeks)	Notes				
		Cycle 1				Cycle ≥2									

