2. OBJECTIVES AND ENDPOINTS

The objectives and endpoints of this study are shown in [Table 4](#) and [Table 5](#).

Table 4: Objectives and Endpoints (Cohorts A and B)

Primary	
To evaluate the objective response rate (ORR) in patients with solid tumors harboring FGFR rearrangements or gastric cancer (including GEJ cancer) harboring FGFR2 amplifications based on independent central review of radiologic images (IRC)	ORR, defined as the proportion of patients experiencing a best overall response of partial response (PR) or complete response (CR) (per Response Evaluation Criteria in Solid Tumors, Version 1.1 [RECIST 1.1]), based on IRC
Secondary	
Key secondary: 
 To evaluate duration of response (DOR) based on IRC Additional secondary: 
 To evaluate ORR based on Investigator assessment To evaluate progression-free survival (PFS), disease control rate (DCR), and overall survival (OS) To assess safety and tolerability 	
 DOR defined as the time from the first documentation of response (CR or PR per RECIST 1.1 based on IRC) to the first documentation of objective tumor progression or death due to any cause, whichever occurs first, based on IRC ORR, defined as the proportion of patients experiencing a best overall response of partial response of PR or CR (per RECIST 1.1), based on Investigator assessment DCR, defined as the proportion of patients experiencing a best overall response of stable disease (SD), PR, or CR (per RECIST 1.1), based on IRC PFS, defined as the time from first dose of study drug to the date of death (any cause) or disease progression (based on IRC), whichever occurs first OS, defined as the time from the date of first dose to the death date Safety based on reported AEs and on-study laboratory parameters, graded according to the National Cancer Institute—Common Terminology Criteria for Adverse Events, Version 5.0 (NCI-CTCAE V5.0),
Exploratory	

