3.3.4. Post-Discontinuation Considerations

Patients who discontinue without documented disease progression should continue to undergo response assessments according to the Schedule of Events (that is, every 8 weeks \pm 7 days) until progressive disease (PD) is documented, new anticancer therapy is initiated, the study is terminated, or the patient dies, withdraws consent, or is lost to follow-up).

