11.5.3.1.2. Secondary Efficacy Analyses

Duration of response is a key efficacy endpoint:

- Duration of response will only be evaluated in patients with an objective response of CR or PR. Patients who are alive and progression-free as of the analysis cut-off date will be censored at their last evaluable response assessment prior to initiation of any new anticancer treatment. Patients who start subsequent anticancer therapy without a prior reported progression will be censored at the last response assessments prior to initiation of the subsequent anticancer therapy.

Additional efficacy endpoints include:

- Overall response rate and DCR based on Investigator assessment will be determined (per RECIST 1.1) as described for the primary analysis of ORR based on independent central review of radiologic images (Section [11.5.3.1.1](#)).
- Progression-free survival will be estimated using the Kaplan-Meier method. Patients who die without a reported disease progression will be considered to have progressed on the date of their death. Patients who did not progress or die will be censored on the date of their last response assessment. Patients who did not have any on-study assessments and did not die will be censored on the first dosing date. Patients who started any subsequent anticancer therapy without a prior reported progression will be censored at the last response assessment prior to initiation of the subsequent anticancer therapy.
- Overall survival will be analyzed in a similar manner to PFS. In the absence of confirmation of death or for patients who are alive as of the OS cut-off date, survival time will be censored at the last known date that the patient was alive.

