5.5.1.2. Secondary Efficacy Analyses

- ORR based on Investigator assessment will be calculated and the 2-sided 95% CI will be derived by the Clopper–Pearson method. The confirmation rule of CR and PR is the same as the primary endpoint.
- DCR based on IRC and Investigator assessment will be calculated and the 2-sided 95% CI will be derived by the Clopper–Pearson method. The confirmation rule of CR and PR is the same as the primary endpoint. A minimum of a 6-week interval is required between the first dosing date and the first SD.
- PFS based on IRC and Investigator assessment will be estimated using the Kaplan–Meier method. Patients who did not progress or die will be censored on the date of their last tumor assessment. Patients who did not have any post-baseline assessments will be censored on the first dosing date. Patients who started any subsequent anti-cancer therapy without a prior reported progression will be censored at the last tumor assessment prior to initiation of the subsequent anti-cancer therapy. The censoring rule for PFS is in [Table 10](#).
- Overall survival will be estimated using the Kaplan–Meier method. In the absence of confirmation of death or for patients who are alive as of the OS cut-off date, survival time will be censored at the last known date that the patient was alive. The censoring rule for OS is in [Table 11](#).
- DOR based on IRC and Investigator assessment will be evaluated only in patients with an objective response of CR or PR. The starting time point is the first documentation of response (CR or PR). DOR will be estimated using the Kaplan–Meier method. Patients who are alive and progression-free as of the data cut-off date will be censored at their last evaluable tumor response assessment. Patients who start subsequent anticancer therapy without a prior reported progression will be censored at the last tumor assessments prior to initiation of the subsequent anticancer therapy. The censoring rule for DOR is described in [Table 12](#).

Table 10: Censoring Rules for Progression-Free Survival (PFS)

No.	Situation	End Date	Outcome
1	Documented PD between scheduled visits	Date of the first assessment that determined PD	PFS event
2	Death during the study with no prior PD	Date of death	PFS event
3	Patients still on treatment without PD as of data cut-off ^a	Date of the last tumor assessment ^b	Censored

No.	Situation	End Date	Outcome

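### Imaging probably ends at local progression while DOR and PFS are read by IRC, so discordant patients are informatively censored and no sensitivity analysis addresses it

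*Protocol*

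**What the plan says.** - **Who decides treatment.** Protocol 8.1.1 says that local results "will be the basis for the continuation or discontinuation of study drug decisions". The sentence concerns study drug, not imaging.
- **When imaging ends.** The response-assessment row of the Schedule of Events (Protocol Table 1) runs "until radiologic PD or initiation of new anticancer therapy (whichever comes first". Protocol 8.1.1 says that patients who stop without documented progression "should continue to undergo response assessments/scans according to the Schedule of Events until PD is documented, new anticancer therapy is initiated"; Protocol 3.3.4 says the same. None of these names the reader whose PD counts. No section provides for IRC confirmation of PD before imaging ends, or for scans after a local PD.
- **Who reads the endpoints.** The key secondary objective in Protocol Table 4 is "To evaluate duration of response (DOR) based on IRC". PFS in that table is also IRC-based. The SAP reports both endpoints by IRC and by Investigator.
- **What happens without IRC progression.** SAP 5.5.1.2 states, for DOR: "Patients who are alive and progression-free as of the data cut-off date will be censored at their last evaluable tumor response assessment". Protocol 11.5.3.1.2 agrees. PFS is censored at the last tumor assessment.
- **The censoring tables.** In SAP Tables 10 and 12 the discontinuation rows cover reasons other than PD or death. New anticancer therapy has its own censoring row. Death without prior PD is an event unless more than 126 days have passed since the last assessment.

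**The concern.** Suppose a responder has radiologic PD by the site's read and IRC does not call PD on that scan. Treatment stops. Documented PD exists, so no further scan is required. The IRC analysis never sees the scan on which it might have called progression, and the patient is censored, normally at the local-PD scan.

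Kaplan-Meier assumes that a censored patient has the same later risk as those still followed. A patient just judged to be progressing is likely to be at higher risk. Removing such patients tends to lengthen IRC DOR and IRC PFS, which is the favourable direction. DOR by IRC is the protocol's key secondary endpoint in a single-arm setting, so a reader needs to know how much of the curve depends on this. The plan offers no analysis that isolates it.

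**Working it through.** **Plan figures.** The plan gives no DOR or PFS figure to reproduce. Its 126-day window does reproduce: (28 × 2 + 7) × 2 = 126.

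**Patients involved.** At the target rates, Cohort A has 25% × 100 = 25 responders and Cohort B has 35% × 35 ≈ 12. At 20% discordance (assumed) that is about 5 and 2–3 responders.

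**Size for DOR.** From the documents: scans every 2 cycles (56 days) and Kaplan-Meier estimation. Assumed: exponential DOR with a true median of 6 months; a share p of responders with local PD one scan before IRC would call PD; no such lead at the first scan after response; other censoring independent.

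Let q be the probability of passing one scan interval without progression.

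- With a month of 30.4375 days, q = 2^(−56/182.625) = 0.8085, so 1 − q = 0.1915.
- Twelve months contains 6 scans. With scanning continued to IRC PD, the 12-month rate is q^6 = 0.279.
- If scans end at local PD, the discordant patients whose IRC PD would fall at scan k left at scan k − 1. From the second scan on, the at-risk share is q^(k−1) × (1 − p + pq) and the event share is (1 − p) × q^(k−1) × (1 − q).
- The hazard per scan is then h = (1 − p)(1 − q) / (1 − p(1 − q)), and the 12-month rate is q(1 − h)^5.
- If local PD counts as an event, the 12-month rate is q^6 × (1 − p(1 − q)).

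Example, p = 0.2: h = 0.8 × 0.1915 / (1 − 0.0383) = 0.1593, and 0.8085 × 0.8407^5 = 0.340.

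| p | Scanned to IRC PD | Scans end at local PD, censored | Same, 30% early deaths counted | Local PD counted as event |
|---|---|---|---|---|
| 10% | 28% | 31% | 30% | 27% |
| 20% | 28% | 34% | 32% | 27% |
| 30% | 28% | 38% | 34% | 26% |

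The fourth column is from simulation. It assumes that 30% of discordant patients die without new therapy, at times uniform between 14 and 126 days after the local-PD scan. The rise is about 2 to 10 percentage points. For a true median of 9 months (q = 0.8679) the same formulas give 43% rising to 46%, 49% and 52%.

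**If IRC would call PD later.** A second simulation had true median 8 months, 20% discordance, scan times varying by ±7 days and 4–24 months of follow-up after response. If IRC would call PD one scan later, 40% becomes 47%. If two scans later, 41% becomes 46%. The gap narrows as the IRC call moves further away. At zero discordance it is nil.

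**Medians.** These are a poor measure here. On a fixed 56-day grid with a true median of 6 months, the Kaplan-Meier median is scan 4 (224 days, 7.4 months) at 0%, 10% and 20% discordance. It jumps to scan 5 (280 days, 9.2 months) at 30%. The 12-month rate is the better gauge.

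**The case against.** The strongest points on the other side are these.

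- **The text does not say that scans stop at local PD.** A reader might infer that it does. The study-drug sentence is not an imaging rule, and the imaging rule names no reader. This stands as a limit on the claim. The local read is nevertheless the only one the protocol describes as acting during treatment, so ending at local PD is the likely practice.
- **Not every discordant patient is censored.** Death within 126 days of the last scan and before new therapy is an event. This reduces the effect without removing it, as the table shows.
- **Equivocal progression may be followed.** Protocol 8.1.4.2 lets treatment continue to the next scheduled assessment, which would give IRC another scan. It is optional and covers equivocal findings only.
- **The tables are not silent on everyone.** Patients who start new therapy have a row. One could also read reasons other than PD as other than IRC PD, and the running text already censors the rest. A stated rule would therefore clarify the main analysis but not change it.
- **Investigator DOR and PFS are planned.** They are free of this mechanism and would partly reveal a gap. But Investigator DOR also changes the responder set and start dates, so a difference cannot be attributed to censoring, and the IRC result stays uncorrected.
- **Consequence is limited.** DOR and PFS carry no hypothesis or threshold. With about 25 responders and a true median of 6 months, sampling alone spreads the 12-month rate from about 9% to nearly 50%. That is fair, but sampling error shows in the confidence interval and this bias does not.

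**Conclusion.** The point holds as a gap in the analysis plan. Local PD without IRC PD leads to informative censoring of IRC DOR and IRC PFS, probably in the favourable direction, and no planned analysis isolates it.

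For DOR with a true median of 6 months, the size is about 2 to 10 percentage points on the 12-month rate. That rests on three assumptions the documents do not supply: 10% to 30% discordance, a one-scan lead, and exponential DOR. It would be smaller if discordance is rare or if IRC would call PD much later.

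A reader might go further and conclude that IRC DOR is inflated. The documents do not show that, because they give no discordance rate and do not name the reader who ends imaging. Nor do they support any effect on the primary endpoint: ORR, its interval and its success rule are not touched by this censoring. This is a cheap improvement worth making, not a flaw in the main design.

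**What to change.** 1. In SAP 5.5.1.2, pre-specify a sensitivity analysis of IRC DOR (in IRC responders, from the IRC response date) and of IRC PFS. In it, a local radiologic PD without IRC PD counts as an event on its date.
2. Report it beside the IRC result, with a table of IRC against local PD status and date. If discordance is negligible, the two results will agree and support the headline.
3. State in SAP Tables 10 and 12 how local PD without IRC PD is handled in the main analysis.

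The local PD dates are already needed for the Investigator analyses, so no extra scans or readers are required. The cost is SAP wording, a little more programming, and a sensitivity DOR that will look somewhat shorter.

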8.1.2. Method of Imaging

The same method of assessment and same technique should be used to characterize each identified and reported lesion at each assessment timepoint. Imaging-based evaluation is preferred to evaluation by clinical examination when both methods have been used to assess the antitumor effect of treatment. All measurements should be recorded in metric notation using a ruler or calipers.

Contrast-enhanced CT scans or MRIs are the preferred methods for response assessments. If a contrast agent is contraindicated in a patient, obtain a non-contrast chest CT and enhanced MRI of the abdomen (and pelvis if clinically indicated). A spiral CT should be performed using a ≤ 5 mm contiguous reconstruction algorithm. Images must be acquired of the chest and abdomen (and pelvis if clinically indicated or obtained at baseline visit) at each time point. Only CT scans and MRI may be used for tumor measurement.

Clinical lesions will only be considered measurable when they are superficial (eg, skin nodules or palpable lymph nodes). In the case of skin lesions, documentation by color photography, including a ruler to estimate the size of the lesion, is recommended.

Ultrasound should not be used to measure tumor lesions that are clinically not easily accessible for overall response evaluation (eg, visceral lesions). Ultrasound is a possible alternative to clinical measurements of superficial palpable nodes, subcutaneous lesions, and thyroid nodules. Ultrasound might also be useful to confirm the complete disappearance of superficial lesions usually assessed by clinical examination. For additional guidance, refer to RECIST 1.1 specifications for standard anatomical radiological imaging.

